4.3.5 Withdrawal of individual subjects

Subjects can leave the study at any time for any reason if they wish to do so without any consequences. The investigator can decide to withdraw a subject from the study for urgent medical reasons.

5. STATISTICAL ANALYSIS

Baseline characteristics will be reported as proportions (%) for categorical variables and numerical (mean with SD or median with IQR) where appropriate. The primary outcome is the recurrence rate at 6 months after resection (binary variable). Because of the nested study design (multiple patients within a cluster of colonoscopists), a logistic mixed-effects models with a random intercept at cluster level (colonoscopists) will be used. The study group (intervention groups vs. control group), previous experience on endoscopic resection of LNPCPs (questionnaires) and lesion complexity (SMSA score) will be used as main variables in the model. For the secondary outcomes, the same mixed model will be used as for the primary outcome, in which a linear mixed model analysis will be used for numerical outcome variables (number of repeat colonoscopies and number of complications) and logistic mixed model analysis for categorical outcome variables (referral to surgery). In case of missing variables multiple imputation as well as complete case analysis will be performed. IBM SPSS statistics version 25 will be used for the analyses.

5.1 Primary study parameter(s)

The primary outcome is the recurrence rate at 6 months after resection (binary variable). Because of the nested study design (multiple patients within a cluster of colonoscopists), a logistic mixed-effects models with a random intercept at cluster level (colonoscopists) will be used. The study group (intervention groups vs. control group), previous experience on endoscopic resection of LNPCPs (questionnaires) and lesion complexity (SMSA score) will be used as main variables in the model.

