After correction for the design effect ($= 1+(m-1)*ICC$, where $ICC = 0.025$ and the mean number of patients per colonoscopist is 35, i.e. $m = 35$), 10% loss in efficiency due to the variation in the number of colonoscopies performed during the study period per colonoscopist (3), and a 20% drop-out risk for patients with LNPCP, the number of LNPCP cases required to detect a difference of 10% (20% local recurrence in the control group vs 10% in the intervention group) with a power of 90% and using a significance level alpha of 5% is 683 per group. This means that 20 colonoscopists per group are required. In the revised protocol, we have increased the power of analyses from 80% to 90%. In conclusion, in the 20 participating centers (10 per arm), a total of 20 colonoscopists will perform approximately 35 endoscopic resections each over 1.5 year.

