4.2 Randomisation, blinding and treatment allocation

Participating centers will be randomized to the *intervention group* vs. *control group*, as detailed in **Figure 1**. To mitigate the effect of contamination, i.e. exchange of knowledge, practical skills between participants, we prefer to randomize centers instead of endoscopists. In each center, two endoscopists will participate in the study. Both the control (n=30 endoscopists) and the intervention group (n=30 endoscopists) will receive an e-learning module regarding the OPTICAL I model focused on optical diagnosis of T1 carcinomas, and assessment of an EMR scar to recognize recurrence. In addition to this, the intervention group will receive an additional EMR training package, consisting of an e-module and a two-day symposium.

We will target our intervention (training) to this specific group because endoscopists at the beginning of their career may be more compliant to implement a change in their practice. An additional questionnaire will be used to provide baseline information regarding total number of endoscopic resections over the past year, resection techniques used (EMR vs ESD), the complication rate (bleeding, perforations) and the referral rate to surgery in order to select 20 endoscopists with comparable experience and endoscopic proficiency. We realize that such selection is associated with difficulty – baseline characteristics among the 2 groups will never be the same. Evaluation of such baseline information is, however, of importance for a meaningful interpretation of the study outcomes.

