5.2 Secondary study parameter(s)

For the secondary outcomes, the same mixed model will be used as for the primary outcome, in which a linear mixed model analysis will be used for numerical outcome variables (number of repeat colonoscopies and number of complications) and logistic mixed model analysis for categorical outcome variables (referral to surgery). In case of missing variables multiple imputation as well as complete case analysis will be performed. IBM SPSS statistics version 23 will be used for the analyses.

Furthermore, we will look at quality of life and cost-effectiveness of endoscopic resection vs. surgical resection of LNPCPs.

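### The primary model has no term for centre, the unit randomised; if outcomes correlate between a centre's two endoscopists, the standard error of the treatment effect is too small

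*Protocol*

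**What the plan says.** Protocol Section 4.2 gives the unit of randomisation: "we prefer to randomize centers instead of endoscopists", to limit exchange of knowledge and skills between participants. It adds: "In each center, two endoscopists will participate in the study". The Summary says the same, and Section 3.1.4 describes the clustering as being at centre level.

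The analysis sections define the cluster differently. Section 5 opens its model with "Because of the nested study design (multiple patients within a cluster of colonoscopists", and Section 5.1 specifies that "a logistic mixed-effects models with a random intercept at cluster level (colonoscopists) will be used". The fixed terms are study group plus two covariates: "previous experience on endoscopic resection of LNPCPs (questionnaires) and lesion complexity (SMSA score) will be used as main variables in the model". Centre appears neither as a random nor as a fixed term, and no centre-robust variance is named. Section 5.2 extends the choice: "For the secondary outcomes, the same mixed model will be used as for the primary outcome".

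The sample size follows the same line. Section 3.1.4 computes the ICC (0.025) for colonoscopists, on the expectation that they vary more than centres do. Its result, "using a significance level alpha of 5% is 683 per group", is for 90% power.

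**The concern.** When treatment is assigned by centre, variation between centres is part of the sampling error of the treatment contrast. A model with a colonoscopist intercept only treats two colleagues in one centre as independent. Any positive correlation between their results is then left out of the standard error. Confidence intervals come out too narrow and p-values too small, for the primary endpoint and for every secondary endpoint that uses the same model.

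The protocol's own design argument points this way. Centres are randomised because colleagues in a centre are expected to influence each other, and the analysis then assumes that they do not. The random effect is named explicitly in Sections 5 and 5.1, so this is a stated choice and not a detail left for a later plan.

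**Working it through.** **Inputs from the protocol.** Recurrence 20% versus 10%, alpha 5% (two-sided assumed, since sidedness is not stated), power 90%, ICC ρ = 0.025 at colonoscopist level, m = 35 lesions per colonoscopist, 10% efficiency loss for unequal cluster size, 20% drop-out (all Section 3.1.4); two endoscopists per centre (Section 4.2). After 20% drop-out, 35 × 0.80 = 28 evaluable lesions per endoscopist.

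**Assumed.** The correlation ρ_b between patients of different endoscopists in the same centre. The protocol gives no value, so it is varied as a share of 0.025.

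**Step 1: reproduce the plan's figure.** The usual two-proportion formula gives 266 per group. The design effect is 1 + 34 × 0.025 = 1.85. Then 266 × 1.85 / 0.90 / 0.80 = 683.5, against 683 stated. The figure reproduces with colonoscopists treated as independent clusters.

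**Step 2: variance seen by the model and actual variance.**
- Model: DE₀ = 1 + (m − 1)ρ
- Actual, two endoscopists per randomised centre: DE₁ = 1 + (m − 1)ρ + m ρ_b
- Actual two-sided error: 2 × [1 − Φ(1.96 × √(DE₀/DE₁))]
- A correct interval is wider by the factor √(DE₁/DE₀)

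Example, m = 35 and a 50% share (ρ_b = 0.0125): DE₁ = 1.85 + 0.4375 = 2.2875; √(1.85/2.2875) = 0.899; 1.96 × 0.899 = 1.763; error 7.8%; interval wider by 1/0.899 = 1.11.

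| Centre share of ICC | DE₁ (m=28; DE₀ 1.675) | Error | DE₁ (m=35; DE₀ 1.85) | Error | Correct interval wider by |
|---|---|---|---|---|---|
| 0% | 1.675 | 5.0% | 1.85 | 5.0% | 0 |
| 10% | 1.745 | 5.5% | 1.94 | 5.5% | 2% |
| 25% | 1.850 | 6.2% | 2.07 | 6.4% | 5–6% |
| 50% | 2.025 | 7.5% | 2.29 | 7.8% | 10–11% |
| 100% (outer bound) | 2.375 | 10.0% | 2.73 | 10.6% | 19–21% |

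**Step 3: power of a test that respects centres.** With 683 per group and m = 35, power is 90% at a 0% share, 89% at 10%, about 87% at 25% and 83% at 50%. Holding 90% would need 266 × DE₁ / 0.72 = 764 per group at 25% and 845 at 50%. If the design effect is taken at 28 evaluable lesions instead of the protocol's 35, power at the same shares is 93%, 92%, 90% and 87%. None of these includes a degrees-of-freedom correction.

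**Step 4: simulation.** A logistic model with a colonoscopist intercept only, no covariates, was fitted to 3,000 null trials per scenario and referred to a t distribution based on the number of colonoscopists. Rejection was 5.4% at zero share, 6.9% at 25% and 8.7–9.2% at 50% (10 centres per arm with m = 35; 15 per arm with m = 28). A t test on centre proportions in the same data, including the 100% share, stayed between 4.8% and 6.3%. The direction agrees with the formula, and the rates run somewhat higher.

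**The case against.** The colonoscopist level is a reasoned choice, not an oversight. Section 3.1.4 expects more variation between colonoscopists than between centres, notes that screening quality measures are standardised at both levels, and considers differences in local care unlikely to matter. If centre variance is in fact zero, the model is adequate. Adjustment for lesion complexity and experience may also absorb part of any within-centre correlation, which neither the formula nor the simulation credits. These points stand, and they limit the size of the problem. They do not remove it, because a smaller variance is not a zero variance and the contamination argument implies some correlation within centres.

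A reader might infer several stronger things that the document does not support:
- That the 5% level is certainly broken. This depends on a centre-level correlation that the protocol never states.
- That the error rate is 10% or more. A 100% centre share means no variation between colleagues in a centre, contrary to Section 3.1.4; it is an outer bound only.
- That uncorrected normal-theory tests add further inflation. The protocol names no test statistic or degrees-of-freedom method, and an analysis plan may settle this.

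The last sentence of Section 3.1.4, with 20 centres and 20 colonoscopists in total, would mean one colonoscopist per centre, and the problem would then vanish. That sentence conflicts with 20 colonoscopists per group in the same section and with two per centre in the Summary and Sections 3.1.4 and 4.2.

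**Conclusion.** The point holds in conditional form. The specified model omits the unit of randomisation, and any positive between-centre variance makes its standard error too small. On the protocol's own expectation (centre share below one half), ICC 0.025 and 28 to 35 lesions per endoscopist, the formula puts the real two-sided error between 5% and about 7.8%. That is a moderate inflation of a confirmatory test, and its exact size cannot be known without a centre-level ICC. It would be too strong to say that a positive result must be rejected on this ground alone: a clear effect would survive an interval 10–11% wider, a borderline one might not. The 90% power claim rests on the same assumption and is likewise conditional.

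**What to change.** In Sections 5, 5.1 and 5.2, specify random intercepts for centre and for colonoscopist nested within centre. State that the treatment effect is tested against between-centre variation with small-sample degrees of freedom suited to the number of centres, and say what is done if the centre variance is estimated as zero.

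In Section 3.1.4, state an assumed centre-level ICC, or a range, and give power for it. Reconcile the counts at the same time: 10 or 15 centres per arm, and 20 colonoscopists in total or 20 or 30 per arm.

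The cost is wording, no new data, and wider intervals as tabulated. If the centre variance is truncated at zero while centre-based degrees of freedom are kept, the test is somewhat conservative: an approximate analysis-of-variance version rejected below 4% at zero centre variance and about 4% at a 25% share. Recruitment need not grow if the larger design applies: 30 endoscopists per arm with 35 resections each is 1,050 per arm, above the 845 needed at a 50% share before a degrees-of-freedom correction. With 20 endoscopists per arm, 20 × 35 = 700, which is short of the 764 needed at a 25% share when the design effect uses 35 lesions.

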5.2 Secondary study parameter(s)

For the secondary outcomes, the same mixed model will be used as for the primary outcome, in which a linear mixed model analysis will be used for numerical outcome variables (number of repeat colonoscopies and number of complications) and logistic mixed model analysis for categorical outcome variables (referral to surgery). In case of missing variables multiple imputation as well as complete case analysis will be performed. IBM SPSS statistics version 23 will be used for the analyses.

Furthermore, we will look at quality of life and cost-effectiveness of endoscopic resection vs. surgical resection of LNPCPs.

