2.1 OBJECTIVES

This project aims to integrate current knowledge and technical expertise on treatment of LNPCPs from leading centers worldwide in the Dutch colonoscopy practice. Development of a standard training program to be supported by education and structured training is a prerequisite for best practice in the management of LNPCPs.

2.1.1 Primary Objective:

To investigate if systematic stepwise training improves the outcome of endoscopic treatment for LNPCPs, i.e. local recurrence (6 months after resection), radical (R0) resection rate, complication rate and referral rate to surgery.

2.1.2 Secondary Objective(s):

The patient's quality of life (QoL) will be assessed. Because a validated questionnaire is not yet available, we will adapt the Medical Outcomes Study Short Form 36 {McHorney, 1993;Ware, 1992} and a colorectal-specific European Organisation for Research and Treatment of Cancer (EORTC) QoL questionnaire {Theodoropoulos, 2013}. Questionnaires will be applied at two or three time points, depending on logistics in the particular hospital (see 5.3; study procedures).

[figure not shown]
To perform a cost-effectiveness analysis to compare post-training endotherapy vs common practice vs laparoscopic surgery for management of LNPCPs.

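### The models for referral to surgery and complications leave out each endoscopist's own baseline referral and complication rates, which the trial already collects; the cost is some precision, not bias

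*Protocol*

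**What the plan says.** Protocol section 5.1 gives the recurrence model as a logistic mixed model with a random intercept per colonoscopist. Besides study group, "previous experience on endoscopic resection of LNPCPs (questionnaires) and lesion complexity (SMSA score) will be used as main variables in the model". Section 5.2, and the same text at the start of section 5, carries this over: "For the secondary outcomes, the same mixed model will be used as for the primary outcome". Referral to surgery is analysed with the logistic version and the number of complications with a linear version. No covariate is added or changed for either.

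Section 4.2 describes the baseline questionnaire. Besides resection volume and technique, it collects "the complication rate (bleeding, perforations) and the referral rate to surgery in order to select 20 endoscopists with comparable experience and endoscopic proficiency". The same paragraph concedes that "baseline characteristics among the 2 groups will never be the same" and says that looking at this information matters for interpreting the results. It does not say that the rates enter any model.

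Both outcomes appear in the primary objective (section 2.1.1), which lists, after recurrence, "radical (R0) resection rate, complication rate and referral rate to surgery".

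**The concern.** The questionnaire yields, for two outcomes, a baseline measure of the same kind, taken at the level where the model has its random intercept. An endoscopist who habitually refers many patients will probably go on doing so. Resection volume and lesion difficulty do not measure that habit, so under the model as fixed it remains unexplained between-colonoscopist variance.

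This matters because the randomised units are few and the protocol (section 3.1.4) expects more variation between colonoscopists than between centres. Two things are at stake: precision for referral and complications, and a pre-specified adjustment if the arms happen to start with different habits, which section 4.2 itself expects. If the arms do differ, adding the adjustment afterwards would be open to challenge as data-driven.

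**Working it through.** **Inputs from the protocol.** ICC 0.025, 35 patients per colonoscopist, 10% efficiency loss, 20% drop-out, 20 colonoscopists per group, and a cited ICC range up to 0.05 (all section 3.1.4). An additional-surgery rate of 8% (section 2).

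**Assumptions.** The protocol gives no planning figures for referral, so I take 8% in controls, halved to 4% by training, with a two-sided 5% test. After drop-out, 35 × 0.8 = 28 patients per colonoscopist are evaluable. Other sections speak of 30 colonoscopists per arm, so that is shown too.

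**The plan's own figure.** For 20% versus 10% at 90% power, the pooled-variance formula gives 266 per group. The design effect is 1 + 34 × 0.025 = 1.85. Then 266 × 1.85 = 492.1; / 0.9 = 546.8; / 0.8 = 683.5. The stated 683 reproduces, and this point does not touch it. Clustering supplies 0.85 of the 1.85, or 46%.

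**Chance imbalance.** Before any selection, the SD of the difference between arms in mean underlying referral rate is √(2 × ICC × 0.08 × 0.92 / k), with k colonoscopists per arm:
- k = 20: 1.4 percentage points at ICC 0.025 and 1.9 at ICC 0.05.
- k = 30: 1.1 and 1.6.

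The assumed effect is 4 points.

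**Power by formula.** Let r be the correlation between the reported baseline rate and the true in-trial rate. The design effect becomes 1 + 27 × ICC × (1 − r²), and the effective n per arm is k × 28 × 0.9 divided by it. For k = 20 and ICC 0.025 the design effect is 1.675 without the covariate and 1.344 at r = 0.7, so 504 / 1.675 = 301 becomes 504 / 1.344 = 375.

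| k per arm, ICC | no baseline rate | r = 0.3 | r = 0.5 | r = 0.7 |
|---|---|---|---|---|
| 20, 0.025 | 54% | 56% | 59% | 64% |
| 20, 0.05 | 41% | 43% | 47% | 54% |
| 30, 0.025 | 72% | 73% | 76% | 81% |
| 30, 0.05 | 57% | 59% | 64% | 71% |

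**How large r can be.** With n past cases and perfectly stable habits, sampling noise limits r² to n × ICC / (1 + (n − 1) × ICC). At ICC 0.025 this is 0.374 for 23.3 cases (35 per 1.5 years) and 0.562 for 50 cases (the yearly volume assumed in the protocol's initial version). So r is at most 0.61 to 0.75.

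**Effect of selecting endoscopists.** Section 4.2 intends to choose endoscopists who are alike, which narrows the proposed covariate. It gives no rule, so the simulations assumed that the 75% or 50% of candidates nearest the median baseline rate are kept. Set-up: 20 colonoscopists per arm, 28 patients each, stable habits, regression on colonoscopist rates with and without the baseline rate.
- ICC 0.025, no narrowing: power rises from about 0.62 to 0.66 (23 past cases) and from 0.62 to 0.70 (50 past cases), a gain of about 4 to 8 points.
- ICC 0.025, 75% kept: 0.60 to 0.61 and 0.63 to 0.65. With 50% kept there is no gain. Overall, about 0 to 2 points.
- ICC 0.05: about 12 to 19 points without narrowing, and about 1 to 7 with it.

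No scenario lost power. Habits that are less than stable give smaller gains.

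**The case against.** The strongest reply is that the covariate in section 5.1 is previous experience taken from questionnaires, and the questionnaire in 4.2 includes the two rates, so they may already be covered. That is possible but not the plain reading: 4.2 names experience and proficiency as separate things, and 5.1 speaks of experience with resection. If the wider meaning is intended, the text still has to say so.

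The second reply is that selecting similar endoscopists removes most of the benefit. This largely stands, and it is why the lower ranges belong beside the higher ones.

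Third, the gains are measured against a model with no covariates, whereas the planned model already adjusts for experience and SMSA score. This stands: the increment over the planned model has not been computed. Using one covariate set for all outcomes is also a legitimate choice, only not the most efficient one here.

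Three stronger inferences should be resisted.
- A reader might infer that leaving the rates out biases the training effect. It does not: chance imbalance between randomised clusters is not bias, and the random intercept carries that variance into the standard error.
- A reader might infer that the rates serve only for selection. Section 4.2 also names interpretation of the outcomes.
- A reader might treat them as past-year rates for LNPCPs. The look-back period is attached to the count ("An additional questionnaire will be used to provide baseline information regarding total number of endoscopic resections over the past year"), which is not limited to LNPCPs, so the 23 to 50 past cases are an inference.

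**Conclusion.** The point holds as a low-cost improvement to two secondary analyses. The protocol fixes their covariates, collects a more relevant one for each, and does not use it in the models. The loss is in precision and in pre-specified protection against chance imbalance.

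For referral, the gain ranges from negligible, if selection makes the endoscopists homogeneous, to worthwhile, if it does not and the ICC is near 0.05. All of this rests on the assumed 8% versus 4%, on 20 colonoscopists per arm, and on how well self-reported rates predict later practice, which the documents do not give. At ICC 0.025 with 20 per arm, the comparison stays below 80% power with or without the covariate.

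For complications only the direction can be argued; no size is claimed. Recurrence is not affected, because the questionnaire items listed in 4.2 do not include it, and the sample size stands.

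**What to change.** In section 5.2 and the matching text in section 5, keep study group, previous experience, SMSA score and the colonoscopist intercept. Add the endoscopist's baseline referral rate as a covariate in the referral model, and the baseline complication rate in the complication model. State that both come from the section 4.2 questionnaire, completed before the centre's allocation is known, and state the period and type of resection to which the rates refer. If previous experience was meant to include these rates, define the term that way.

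The cost is a sentence or two of wording and one between-cluster degree of freedom per model, with no new data. If the self-reported rates are noisy, or uniform after selection, little is gained.

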To ensure en-bloc resection of lesions with high suspicion of malignancy, the endoscopic submucosal dissection (ESD) technique should be adopted. Practical performance of ESD is however difficult and requires a long and steep learning curve, additional equipment and longer procedural time {Saito, 2001}. Risk of perforation is also higher for ESD vs EMR: 5.4% (1.3%-20.4%) vs. 0.7% (0%-6%) {Tanaka, 2013}. A strategic multistep plan is therefore

required to implement ESD in the Western endoscopy practice {Sanduleanu, 2016}. Pre-treatment diagnosis of the depth of submucosal (SM) invasion which takes into consideration lesion appearance, epithelial surface pit-pattern and vascular pit-pattern is a key-step towards successful endotherapy {Yamada, 2016}. Additional technical and non-technical (logistic, strategic) skills are required. As this takes considerable time, referral to specialized centers where complex endotherapy can be performed in a timely manner is recommended in the meantime {Rutter, 2015}. For example, in the case of a LNPCP ≥ 20 mm in size, with a non-invasive pit-pattern, the lesion is likely an adenoma, or intramucosal cancer (Tis) or superficial submucosal invasive carcinoma (T1a cancer, i.e. SM invasion depth $< 1000\mu\text{m}$, sm1) with a very low risk of lymph node metastasis and ESD is the preferred therapy {Kitajima, 2004; Nakajima, 2013}. When deep submucosal invasive cancer (T1B cancer, i.e. SM invasion depth $> 1000\mu\text{m}$, sm 2-3) is suspected, given the high risk of lymph node metastasis, surgery is recommended {Yamada, 2016}.

Differentiation of an invasive from a non-invasive epithelial surface pit-patterns is challenging and ideally requires magnifying chromoendoscopy {Hayashi, 2013}. A large prospective study at the National Cancer Center in Tokyo (Japan) showed a sensitivity, specificity and diagnostic accuracy of differentiating mucosal cancer or superficial (sm1) invasion from deeper (sm2-3) invasion using magnifying chromoendoscopy of 85.6%, 99.4% and 98.8%, respectively {Matsuda, 2008}. A recent study of the same group showed the importance of a thorough macroscopic examination. Because both *granular type* LSTs with a large nodule or depression and *non-granular type* LSTs are associated with a substantial risk of submucosal (SM) and multifocal invasion, *en-bloc* endoscopic resection is the preferred therapy in such cases {Yamada, 2016}.

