4.1.2 Secondary study parameters/endpoints (if applicable)

- Radical (R0) resection rate
- Complication rate
- Number of repeat colonoscopies
- Referral rate to surgery
- Quality of life
- Cost-effectiveness

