- b. Zoom
- c. Zoom with advanced imaging modality (e.g. NBI, I-scan)

STEP 2: ENDOSCOPIC MUCOSAL RESECTION

1. EMR documentation in endoscopy report

- a. Lifting fluid → NaCl / Gelofusin/ Venofundin

- b. Dye included in the injection fluid →yes/no
- c. Adjuvant adrenalin in lifting fluid → yes/no?
- d. En-bloc or piecemeal?
- e. Number of pieces [n = ... / >10 fragments]
- f. Intraprocedural bleeding yes/no?
 - i. Number of intraprocedural bleedings
 - ii. Treatment intraprocedural bleeding
 - 1. Clipping
 - 2. Snare tip coagulation
 - 3. Coagulation grasper
 - 4. Adrenalin injection
- g. Residual tissue after EMR yes/no?
 - i. In case of residual tissue, adjunctive treatment?
 - 1. Cold avulsion with biopsy forceps
 - 2. Cold avulsion with thermal ablation (CAST)
 - 3. Hot avulsion
 - 4. Snare tip coagulation
 - 5. Suck and snare
 - 6. APC
- h. Adjuvant treatment performed to prevent recurrence yes/no?
 - i. Argon plasma coagulation
 - 1. Borders (y/n)
 - 2. Scar surface (y/n)
 - ii. Snare tip soft coagulation
 - 1. Borders (y/n)
 - 2. Scar surface (y/n)

2. Tattoo 2 cm distal at the same side (to make sure the scar can be retrieved during surveillance colonoscopy)

3. Photo/videodocumentation

- a. Recording first 5 EMRs (intervention group)
- b. Photodocumentation of the scar
 - i. Before adjunctive treatment
 - ii. Before adjuvant treatment
 - iii. After adjuvant treatment

STEP 3: AFTER COLONOSCOPY

- 1. Informing the patient about the study

2. Providing the information package
3. Note patient data on study list (patient number, sex, birthdate)
4. Schedule 6 month FU colonoscopy

STEP 4: SURVEILLANCE COLONOSCOPY AFTER 6 MONTHS

1. Endoscopy report

- a. Recurrence yes/no?
- b. Unifocal or multifocal [n]
- c. Size of largest recurrence (in mm)
- d. In case of recurrence, treatment yes/no?
 - i. Re-EMR
 - ii. Cold avulsion
 - iii. Cold avulsion with snare tip coagulation (CAST)
 - iv. Hot avulsion
 - v. Suck and snare
 - vi. eFTR
 - vii. ESD
 - viii. APC
 - ix. Snare tip soft coagulation (STSC)

2. Biopsy the scar

- a. Take a biopsy every 5 mm [e.g. in a scar of 18mm, 3 biopsies are taken]
- b. Present every biopsy in a separate PA jar

3. Photodocumentation

- a. Scar [white light, zoom and advanced imaging modality]

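### Complications are analysed as a number with a linear mixed model, although the endpoint and stated safety comparison is the complication rate

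*Protocol*

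**What the plan says.** Protocol section 4.1.2 lists "Complication rate", "Number of repeat colonoscopies" and "Referral rate to surgery" among the secondary endpoints. The complication rate also appears in the summary and in the primary objective (2.1.1). Section 3 sets safety, measured by the complication rate, beside effectiveness, measured by local recurrence. No section defines it further. Section 4.2, describing the baseline questionnaire, explains complications as bleeding and perforations.

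On analysis, section 5.2 begins: "For the secondary outcomes, the same mixed model will be used as for the primary outcome". It then divides the outcomes: "a linear mixed model analysis will be used for numerical outcome variables (number of repeat colonoscopies and number of complications", against "logistic mixed model analysis for categorical outcome variables (referral to surgery". Section 5 has the same text. Sections 5 and 5.1 call the recurrence rate a binary variable.

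The EMR checklist in Appendix A, Step 2, records "Number of intraprocedural bleedings". The only complication frequency in the document is in the introduction: "Risk of perforation is also higher for ESD vs EMR: 5.4% (1.3%-20.4%) vs. 0.7% (0%-6" (percent).

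**The concern.** Between the endpoint list and the analysis section, complications change from a rate to a number. No other endpoint called a rate and given a named model changes in this way. A linear mixed model of the number compares mean events per patient. A reader of the results would expect to learn what share of patients, or of resections, had a complication in each arm.

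The difference matters when a patient can have several events. If the bleeds counted in the checklist enter the total, repeated bleeds in one patient can outweigh single perforations in others. A linear model with constant normal residual variance is also an awkward description of an outcome that may be zero for most patients. What is at stake is the meaning and readability of the safety comparison.

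**Working it through.** **1. The protocol's own pattern**

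| Endpoint as listed | Outcome in the analysis | Model |
|---|---|---|
| Recurrence rate | binary | logistic mixed |
| Referral rate to surgery | categorical | logistic mixed |
| Complication rate | number | linear mixed |
| Number of repeat colonoscopies | number | linear mixed |

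Only the third row has an endpoint that differs from what is analysed. In the fourth row they agree, so only the choice of distribution is open.

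**2. Why the two measures can disagree.** Take one patient with three bleeds in one arm and two patients with one perforation each in the other. The totals are 3 against 2; the numbers of affected patients are 1 against 2. The ordering reverses. This applies only if the checklist bleeds count as complications, which the protocol does not say.

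**3. The stated sample size.** Inputs from section 3.1.4: 20% against 10%, alpha 5% (taken as two-sided), power 90%, ICC 0.025, m = 35, 10% efficiency loss, 20% drop-out.
- Per group before inflation: [1.96·√(2·0.15·0.85) + 1.2816·√(0.20·0.80 + 0.10·0.90)]² / 0.10² ≈ 266
- Design effect: 1 + 34·0.025 = 1.85, and 266·1.85 = 492.1
- 492.1 / 0.9 / 0.8 = 683.5, against 683 stated

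The figure reproduces. It rests on recurrence alone, so nothing here changes it.

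**4. Sparsity at the cited perforation rates.** For a yes/no outcome with rate p, skewness is (1 − 2p)/√(p(1 − p)) and variance is p(1 − p).

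| | p = 0.7% (EMR) | p = 5.4% (ESD) |
|---|---|---|
| Expected events in 683 | 4.8 | 36.9 |
| Skewness | 11.8 | 3.9 |
| Colonoscopists with no event in 35 cases, (1 − p)^35 | 78% | 14% |
| Variance at p / variance at p/2 | 1.99 | 1.94 |

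After 20% drop-out, 683·0.8 = 546 patients give 546·0.007 = 3.8 events, hence about 4 to 5 EMR perforations per arm. Halving the rate roughly halves the variance, so constant residual variance does not hold when training works.

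**5. Does the linear model's test fail?** A linear mixed model (REML, random intercept per colonoscopist) was fitted to simulated counts, 1,500 runs per scenario. Assumptions not in the protocol: unequal cluster sizes averaging about 27 evaluable patients, between-colonoscopist SD 0.5 on the log scale, three complexity levels each doubling the rate, and Poisson counts given these. With 20 colonoscopists per arm and no effect:

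| Rate | Rejection | Coverage | Runs with a negative fitted number | Colonoscopist variance estimated as zero |
|---|---|---|---|---|
| 0.7% | 3.6% | 96.2% | 49% | 53% |
| 2% | 4.4% | 95.6% | 28% | 37% |
| 6% | 4.7% | 95.3% | 9% | 11% |

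When the intervention halves a control rate of 2% to 10%, negative fitted numbers occur in 44% to 50% of runs and coverage is 94.5% to 95.1%.

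The protocol also mentions 30 endoscopists per arm. With that number (about 28 patients each), rejection under no effect is 3.5%, 4.5% and 6.2% at the three rates, and coverage over all scenarios is 93.8% to 96.5%. The Monte Carlo error at 5% is √(0.05·0.95/1500) = 0.56 points. The 6.2% is about two such errors above 5%, in one of six scenarios without an effect, and does not establish inflation.

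**The case against.** The strongest defence is that complication rate is undefined and could mean events per patient. A difference in mean counts would then be the endpoint itself. That reading cannot be excluded, but the protocol treats its other two modelled rates as yes/no outcomes, and nothing defines this one differently. A separate SAP might refine the model, but it would have to depart from what sections 5 and 5.2 fix.

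Four stronger readings are tempting, and the documents do not support them.

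- **The intervals are unreliable.** The simulation shows near-nominal rejection and coverage. Negative fitted values and zero variance estimates indicate poor fit, not an invalid test. With 4 or 5 events per arm an ordinary logistic mixed model would struggle too.
- **The linear analysis costs power.** The direction depends on assumptions the protocol does not make. Take effective n = 683·0.72/1.85 = 266 per arm, any complication 12% against 6%, and 1 + Poisson(1) events per affected patient. Counts give z = 0.12/√(0.828/266) = 2.15, power 58%; the binary outcome gives z = 0.06/√(0.162/266) = 2.43, power 68%. If events per affected patient fall to 1 + Poisson(0.5) under intervention, counts give z = 0.15/√(0.699/266) = 2.93, power 83%, and the order reverses.
- **Complications as a whole are rare.** The 0.7% is perforation only. No frequency is given for bleeding or for all complications.
- **Repeat colonoscopies share the fault.** That endpoint is listed as a number, no frequency is given, and whether the scheduled 6-month examination counts is not stated. Neither a mismatch nor rarity is shown.

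It is also true that a yes/no outcome scores one minor bleed the same as one perforation. Only separate reporting addresses severity.

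**Conclusion.** The point holds in a limited form. As written, the planned analysis of complications estimates a difference in mean events per patient, whereas the endpoint and stated safety comparison is a rate. This rests on reading the rate as a proportion, which the handling of recurrence and referral supports. The linear model is also poorly suited to sparse, skewed, non-negative counts whose variance changes with the mean. How poorly depends on the overall complication frequency, which the protocol does not give.

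No material type I error inflation or loss of coverage is shown. The simulation did not add clustering of several events within one patient. That repeated bleeds would dominate the comparison is a possibility conditional on their being counted, not an established result. The primary analysis and sample size are unaffected.

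**What to change.** In sections 5 and 5.2:

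- Define the complication rate as the proportion of patients (or of resections; choose one unit) with at least one complication. Analyse it with the same logistic mixed model as recurrence and referral to surgery.
- State whether intraprocedural bleeds count as complications.
- Report bleeding and perforation separately, with an exact or penalised method where events are few, as expected for EMR perforation.
- If the number of complications is kept, make it a supportive analysis.
- For the number of repeat colonoscopies, a Poisson or negative-binomial mixed model would suit a count better. This is an improvement, not the correction of a demonstrated error.

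The data are already to be collected, and neither the sample size nor the primary analysis changes. The cost is a wording amendment to the protocol, to be notified to the ethics committee under section 7.3.
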